### 4. HYPOTHESIS

The hypothesis is based on the primary objective and one primary outcome, which is proportion of women achieving vaginal delivery within 36 hours of intervention.

Null hypothesis states that Dilapan-S is inferior to Misoprostol in efficacy for cervical ripening for induction of labor.

 $H_0: p_M - p_D \ge \delta$ 

Alternative hypothesis states that Dilapan-S is non-inferior to Misoprostol in efficacy for cervical ripening for induction of labor.

 $H_A: p_M - p_D < \delta$ 

### 4.1. INTERIM ANALYSIS

The data was reviewed by Data and Safety Monitoring Board (DSMB) to ensure the safety aspects of the study. Data was presented without revealing the randomization.

### 5. DETERMINATION OF SAMPLE SIZE

The study is powered at 85% for detecting the primary outcome with a type 1 error at 2.5% for one-sided test.

### 6. STATISTICAL PRINCIPLES

### 6.1. GENERAL STATISTICAL CONSIDERATIONS

The statistical analyses will be performed in accordance with ICH E9 guideline (ICH E9, 1998) and is based on all collected data. Statistical analyses will be performed at the 5% significance level.

The quantitative variables will be summarized using the following parameters:

- Number of non-missing data,
- Mean,
- Standard deviation,
- Median,
- Minimum and Maximum (range),
- First and Third quartiles (interquartile range).

The categorical/qualitative variables will be summarized using the following parameters:

- Number of non-missing data,
- Frequencies and percentages.

All collected data will be presented in data listings.

### 6.1.1. MEASURES TO ADJUST FOR MULTIPLICITY, CONFOUNDERS AND HETEROGENEITY

Only one primary objective, outcome and pair of hypotheses is set. Subgroup/Covariate analyses will be introduced as sensitivity analysis if appropriate.

#### 6.1.2. DESIGN TECHNIQUES TO AVOID BIAS

This is a prospective, randomized, controlled, open-label clinical trial to assess the performance and safety.

### 6.1.3. MISSING VALUES, OUTLIERS AND OTHER DATA CONVENTIONS

The analysis will be conducted per protocol.

Besides, for primary and secondary objectives that explore trends over time, in the case of intermediate or final missing data, these will be replaced in accordance with the "intention to treat" method (ITT) and in particular by using the LOCF (last observation carried forward) method.

### 6.2. ANALYSIS POPULATIONS

### 6.2.1. SAFETY POPULATION

The Safety population will be comprised of all subjects in whom Dilapan-S® was inserted or who received at least one dose of misoprostol. This population will be based on the actual treatment received if this differs from that to which the subject was randomized. This population will be used for the analysis of safety data.

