To ensure safety of the subjects, local monitoring will be completed by the Quality Assurance Monitor for the Department of Obstetrics and Gynecology for this Investigator/Peer study. At each scheduled monitoring visit, the QA will randomly select a representative number of study subject charts to be reviewed. Additional monitoring will be based on the initial monitoring review. An independent monitor appointed by the Funder {Medicem} will review the data periodically throughout the duration of trial to ensure the subject safety, data quality and protocol compliance.

Biostatistics

Primary/Null Hypothesis, to be rejected is as follows: Dilapan is inferior to Misoprostol in efficacy for cervical ripening for induction of labor.

Basic principles for an evaluation of the study are presented in this section. It is concerned mostly about the study populations and evaluation of the study endpoints, more detailed

Version 3.1 dated SEP 4, 2020

COMRED

description of how to analyze collected data will be specified in statistical analysis plan (SAP) which will be written and approved before the database lock.

Additionally, the primary outcome will be analyzed on each stratification factor. Mantel-Haenzsel test will be used to test the difference between the subgroups. This testing will be done for exploratory purposes only.

Study populations

Safety Population

The Safety population will be comprised of all subjects to whom Dilapan-S[®] was inserted or who received at least one dose of misoprostol. This population will be based on the actual treatment received if this differs from that to which the subject was randomized. This population will be used for the analysis of safety data.

Intent-to-treat Population (ITT)

ITT includes all patients that were randomized into the study. ITT subjects will be analyzed in accordance with their randomized study treatment (i.e. in the treatment group they were originally allocated, regardless of treatment actually received). ITT will be used for evaluation of the baseline characteristics and as the primary population for efficacy assessments.

Per Protocol Population (PP)

PP is a subset of ITT patients who received study treatment. Following patients will be excluded from the PP population:

- 1. Patients with major protocol violation affecting the efficacy endpoints. Major protocol violations include (but are not limited to): a. Treatment assignment error
 - b. Violation of one or more inclusion/exclusion criteria

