### 2. STUDY PROCEDURES

After randomization all participants will undergo assessment as per the floor protocol including Bishop score. Patients will have either 1-5 Dilapan-S® rods inserted into their cervix by the providers or receive 25 mcg of misoprostol orally every 2 hours to a maximum of 6 doses over 12 hours. Patients will be examined after 12 hours, Dilapan-S® rods will be removed and Bishop score will be reassessed. Patients in both groups will be evaluated for artificial rupture of membranes and initiation of oxytocin for inducing uterine contraction. A diagnosis of failed IOL will be made if patient does not go into active labor within 24 hours after initiation of Oxytocin and AROM. Intrapartum management will be according to institutional guidelines. All study participants will be contacted by phone 2 weeks after enrollment to find out if they needed any additional treatment following discharge. All study patients will be asked to fill out a questionnaire regarding their experience with the method of induction. Data will be collected by chart review and analysed based on the outlined statistical plan.

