# 3.2. SECONDARY OUTCOMES

Individual and composite maternal and fetal outcomes including overall vaginal delivery rate, cesarean section rate, Bishop score after cervical ripening, infections, postpartum hemorrhage. Neonatal outcomes include Apgar scores, NICU admission and sepsis.

Secondary endpoints are:

- Overall vaginal delivery rate in each group
- Rate of caesarean deliveries in each group
- Rate of operative deliveries (vaginal plus caesarean)
- Bishop score at 12 hours after the intervention and change in Bishop score
- Percentage of subjects who did not receive all 6 misoprostol doses
- Percentage of subjects with failed Dilapan-S insertion
- Percentage of subjects delivering vaginally in 24 hours after the initiation of intervention

- Delivery time
- Initiation of cervical ripening to delivery time
- Initiation of oxytocin to delivery time
- Total length of hospital stay
- Maternal outcomes:
  - Chorioamnionitis
  - Endometritis within 2 weeks after delivery
  - Postpartum haemorrhage (EBL>1000cc and/or drop in HCT by 10 points)
  - 3rd and 4th degree lacerations
- Neonatal outcomes:
  - Apgar score <7 at 5 min
  - Cord arterial blood pH and Cord arterial blood pH <7
  - Cord arterial blood base excess and Cord arterial blood base excess > -12mmol/l
  - NICU admission within 2 weeks after study intervention
  - Antibiotic use within 2 weeks after study intervention

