# 3.3.2. COMPLICATIONS SPECIFIC TO DILATOR INSERTION

- Vaginal bleeding
- Rupture of membranes
- Cervical laceration
- Excessive pain causing need for analgesia during cervical ripening
- Vasovagal reaction during insertion of the device
- Entrapment of the device
- Fragmentation of device during removal or insertion
- Retraction of device into uterine cavity.
- Failure to insert Dilapan-S®

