#### Safety data

- Table 14.3.1 Summary statistics of Undesirable Side Effects
- Table
   14.3.2
   Summary statistics of Complications Specific to Dilator Insertion

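### As the safety population is defined, a complete failure to insert Dilapan-S cannot appear in the Dilapan-S column of the insertion-complication table (SAP 6.2.1, 3.3.2, Table 14.3.2)

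*SAP*

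**What the plan says.** - **Population.** SAP 6.2.1 admits women in whom Dilapan-S "was inserted or who received at least one dose of misoprostol. This population will be based on the actual treatment received". The Safety Population paragraph of the protocol has the same entry rule ("was inserted or who received at least one dose of misoprostol"), also with grouping by treatment received. On its use, SAP 6.2.1 states: "This population will be used for the analysis of safety data".
- **Endpoints.** SAP 3.3.2 lists complications of dilator insertion as safety endpoints. Among them are "Failure to insert Dilapan-S" and "Vasovagal reaction during insertion of the device". The protocol's own list (Exploratory research questions) does not contain failure to insert; the SAP added it.
- **Table.** Table 14.3.2, listed under safety data, is titled "Summary statistics of Complications Specific to Dilator Insertion". The list of tables gives neither its population nor its columns. SAP 7.4 asks for numbers of cases and proportions of patients.
- **Rods.** SAP 2 says "Patients will have either 1-5 Dilapan-S" rods inserted, so a single rod is an insertion.
- **A parallel endpoint.** SAP 3.2 also has "Percentage of subjects with failed Dilapan-S insertion" as a secondary endpoint.

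**The concern.** Entry to the Dilapan-S safety group depends on success of the step whose failure is an endpoint. A woman in whom an attempt is made and no rod is placed is not someone in whom Dilapan-S was inserted. She reaches the safety population only through a misoprostol dose, and then under misoprostol.

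Two things are at stake. The failure-to-insert row would show no complete failures in the one group where they can be read as a property of the device. And a vasovagal reaction, cervical laceration, bleeding or membrane rupture during such an attempt would be dropped or shown under the comparator. The protocol says it collects these events to assess Dilapan-S safety because good clinical data are scarce, so the denominator matters.

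**Working it through.** **Arm size.** The protocol (Study Design) needs 153 assessable women per arm with a 5% allowance: 153 × 1.05 = 160.65, rounded up to 161, and 2 × 161 = 322, the stated total. So 161 women are taken as randomised to Dilapan-S, all with an attempted insertion. The plan gives no insertion-failure or complication rate; every rate below is an assumption.

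**Step 1: apply the rule.**

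| After an attempted insertion | In safety population | Column |
|---|---|---|
| No rod, no misoprostol | No | None |
| No rod, at least one misoprostol dose | Yes | Misoprostol |
| At least one rod, no misoprostol | Yes | Dilapan-S |

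A complete failure adds 0 to both numerator and denominator of the Dilapan-S column. Partial insertion, or failure followed by success, falls in the last row and can still register.

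**Step 2: the failure-to-insert row.** Let f be the number of complete failures.

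| Assumed rate | 161 × rate | f | Over all attempts | Dilapan-S safety column |
|---|---|---|---|---|
| 1% | 1.6 | 2 | 2/161 = 1.2% | 0/159 |
| 3% | 4.8 | 5 | 5/161 = 3.1% | 0/156 |
| 5% | 8.1 | 8 | 8/161 = 5.0% | 0/153 |

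(The 153 in the last line is 161 − 8; its match with the assessable number per arm is a coincidence.)

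**Step 3: other complications of the attempt.** Let i be the rate in failed attempts and s the rate in successful insertions. The rate over all attempts is [s(161 − f) + i·f]/161. The reported rate is s. The understatement is therefore f(i − s)/161, in percentage points:

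| f | i = 25%, s = 10% | i = s | i = 10%, s = 15% |
|---|---|---|---|
| 2 | 0.19 | 0 | −0.06 |
| 5 | 0.47 | 0 | −0.16 |
| 8 | 0.75 | 0 | −0.25 |

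For f = 8 and the first case: 8 × 0.15/161 = 0.75 points. A negative value means the device looks worse than it is.

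**Step 4: events that need a rod in place** (entrapment, retraction). The smaller denominator raises the rate slightly: 8 events would read 8/153 = 5.2% instead of 8/161 = 5.0%.

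**Step 5: the misoprostol column.** If m women with a failed attempt take misoprostol, and b is that group's background rate, its rate moves by m(i − b)/(161 + m). With m = 8: i = 25%, b = 10% gives 8 × 0.15/169 = 0.71 points; i = b gives 0; i = 5%, b = 10% gives −0.24 points.

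**The case against.** The strongest reply is that the event has another home. Failed insertion is a secondary endpoint in SAP 3.2. SAP 7.3 calls for secondary percentages in both arms, and SAP 6.2.2 makes the intention-to-treat population primary for efficacy. If that population is used, every complete failure counts in its randomised arm. This largely stands: a reader might infer that failed insertions vanish from the analysis, and the documents do not support that. The route is probable rather than certain, because no population or dedicated table is named for this endpoint, SAP 6.1.3 says the analysis is per protocol, and the per-protocol set requires treatment received. It also counts failures only, not the complications of failed attempts.

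Second, a woman who goes on to misoprostol is not lost. Her failure can appear in the misoprostol column, where its origin is obvious. That stands for the failure row, but not for bleeding or membrane rupture, which would not be recognisable there as results of an attempt.

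Third, neither insertion nor failed insertion is defined, and Table 14.3.2 could use another population. True, but SAP 6.2.1 is the only stated rule for safety data, and the SAP itself treats insertion and failure to insert as different things. If attempts were meant, the text should say so.

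Fourth, data listings (SAP 6.1) and the protocol's reporting of device-related serious events and product problems would show individual cases. They would, but they are not a planned summary over all attempts.

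**Conclusion.** The point holds in a limited form. If Table 14.3.2 follows SAP 6.2.1 as written, complete insertion failures in the Dilapan-S column are zero by construction, and complications of those attempts are missing from the Dilapan-S rates. This should be corrected, but it is a flaw in descriptive safety tables: no test, sample size or non-inferiority conclusion changes.

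The direction is known only for the failure-to-insert row, which would look too favourable (0 instead of 1.2% to 5.0% under the assumed rates). A reader might infer that the rule makes the device look safer overall. The documents do not support this: for the other complications the shift is positive, zero or negative depending on whether failed attempts carry more events than successful ones, and no such figures are given. Nor does every failed insertion escape the column; only those with no rod placed do.

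The conclusion assumes that inserted means at least one rod placed and that Table 14.3.2 uses the safety population by treatment received.

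**What to change.** Change the SAP only; the protocol's list does not contain the failure endpoint, so its population paragraph can stay.

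1. State that SAP 3.3.2 and Table 14.3.2 are reported over all women in whom Dilapan-S insertion was attempted. Show these women as the Dilapan-S column whether or not a rod was placed or misoprostol followed.
2. Give one definition of failed insertion for SAP 3.2 and 3.3.2, saying whether partial insertion, or failure followed by success, counts.
3. Leave SAP 3.3.1 events on the existing safety population by treatment received. A footnote to Table 14.3.1 should give the number of women with an attempt, no rod and no misoprostol, since they remain outside it.

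The cost is a few lines of text and a little more programming. Attributing bleeding or membrane rupture in women with both exposures needs some judgement and event timing; the case report form is not shown, so whether timing is recorded is unknown. The failure-to-insert row may look less favourable than it would under the present rule.

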### 6.2.2. INTENT-TO-TREAT POPULATION (ITT)

ITT includes all patients that were randomized into the study. ITT subjects will be analysed in accordance with their randomized study treatment (i.e. in the treatment group they were originally allocated, regardless of treatment actually received). ITT will be used for evaluation of the baseline characteristics and as the primary population for efficacy assessments.

#### 6.2.3. PER PROTOCOL POPULATION (PP)

PP is a subset of ITT patients who received study treatment. Following patients will be excluded from the PP population:

- 1. Patients with major protocol violation affecting the efficacy endpoints. Major protocol violations include (but are not limited to):
  - a. Treatment assignment error
  - b. Violation of one or more inclusion/exclusion criteria
  - c. Use of forbidden medication
- 2. Patients who were prematurely withdrawn
- 3. Patients with missing data for the evaluation of the primary endpoint

This list can be extended based on a knowledge of other serious issues appearing in the data.

PP population will be used for evaluation of efficacy endpoints as a sensitivity analysis.

### 7. STATISTICAL METHODS

#### 7.1. ANALYSIS OF BASELINE CHARACTERISTICS

Demographic data will be summarized.

#### 7.2. ANALYSIS OF THE PRIMARY ENDPOINT

The primary outcome is the proportion of subjects achieving vaginal delivery within 36 hours after the initiation of the cervical ripening in Misoprostol and Dilapan-S® groups. Proportion of patients in each group and their difference will be calculated. One-sided 97.5% confidence interval adjusted for the stratification factors (parity and gestational age) will be calculated for the difference in the proportions and conclusion about non-inferiority will be drawn from it taking into consideration a 10% non-inferiority margin. Unadjusted confidence interval will be calculated as well.

Additionally, the primary outcome will be analysed for each stratification factor. Mantel-Haenszel test will be used to test the difference between the subgroups.

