Non-inferiority unblinded randomized controlled trial where subjects will be randomized in a ratio of 1:1 to Dilapan-S[®] and misoprostol groups. We decided to use the non-inferiority design as Misoprostol is considered as one of the accepted and standard treatments for induction of labor in United States. Our assumptions for the trial are based on results of PROBAAT-II trial, a large well designed randomized trial conducted in EU for studying efficacy of mechanical and pharmacological methods for labor induction. Assuming a rate of vaginal delivery within 36 hours to be 65% for Misoprostol and 71% for mechanical method (based on data on transcervical Foley catheter in PROBAAT-II [3] and a recent trial comparing Foley catheter to Dilapan-S[®] for cervical ripening done by Saad et al. [12]), with a non-inferiority margin of 10 % and an expected screen failures rate of 5%, a total of 322 subjects will need to be randomized in ratio 1:1 to Dilapan-S[®] vs Misoprostol group. 153 eligible and assessable subjects are needed in Dilapan-S[®] group and 153 in Misoprostol group for analysis. The study is powered at 85% for detecting the primary outcome with a type 1 error at 2.5% for one-sided test.

Objective for the trial

To assess efficacy of cervical ripening with Dilapan-S[®] or Misoprostol in women undergoing induction of labor.

Primary research question (primary endpoint)

Proportion of subjects achieving vaginal delivery within 36 hours after the initiation of the cervical ripening in Misoprostol and Dilapan-S[®] group.

Rationale: The authors of PROBAAT-II study make the valid point that as an outcome of labor induction, giving birth vaginally is more important than how quickly it happens; therefore 24 hours may not be a long enough time for appropriate assessment. Indeed, the effect found in the PROBAAT-II study would have been reversed had the outcome been measured by assessing vaginal delivery within 36 hours. There is therefore a call to standardize the outcome measure in IOL trials to a vaginal delivery within 36 hours [6], particularly when mechanical methods are employed.

Secondary research questions (secondary endpoints)

- Bishop score at 12 hours after the intervention
- Percentage of subjects delivering vaginally in 24 hours after the initiation of intervention
- Overall vaginal delivery rate in each group
- Rate of operative deliveries
- Rate of cesarean deliveries in each group.
- Total length of hospital stay

Maternal outcomes:

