#### 3.1. PRIMARY OUTCOME

Proportion of women achieving vaginal delivery within 36 hours of intervention.

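### The Safety population omits women whose Dilapan-S insertion fails, although failure to insert is a safety endpoint; the 36-hour clock is also undefined for women in either arm who never start ripening

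*SAP*

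**What the plan says.** **Safety.** SAP 3.3.2 lists "Failure to insert Dilapan-S" among the complications of dilator insertion, next to bleeding, cervical laceration and vasovagal reaction. SAP 3.2 adds the secondary endpoint "Percentage of subjects with failed Dilapan-S insertion". Neither failure endpoint is in the Protocol's lists. SAP 6.2.1 keeps the Protocol's population almost unchanged: "The Safety population will be comprised of all subjects in whom Dilapan-S" was inserted, plus those with at least one misoprostol dose, grouped by treatment actually received and used for the safety data. SAP 7.4 promises the number of cases and the proportion of patients.

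**Primary endpoint.** SAP 7.2 counts vaginal delivery "within 36 hours after the initiation of the cervical ripening". SAP 3.1 words it as "Proportion of women achieving vaginal delivery within 36 hours of intervention". Neither document says whether the start is randomisation, the insertion attempt, successful placement, the first dose or a later method. SAP 6.2.2 states that "ITT includes all patients that were randomized into the study", analysed as allocated, and makes this the primary efficacy population. Women with a missing primary endpoint are excluded only from the Per Protocol population (SAP 6.2.3). The LOCF rule in SAP 6.1.3 is aimed at trends over time and supplies no start time.

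**The concern.** The SAP added failed insertion as an outcome but did not adapt the population in which safety outcomes are counted. A safety endpoint is of little use if the women who meet it fall outside its denominator. What is at stake is the Dilapan-S safety profile: how often placement fails, and what harm a failed attempt causes.

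The same women expose the gap in the primary endpoint. They stay in ITT, but the plan does not say when their 36 hours begin. The trial is open-label, so without a written rule the choice would be made with allocation known. In a non-inferiority comparison with a 10-point margin, a small shift in one arm can matter.

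**Working it through.** **1. Safety population: the sections side by side**

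Take a woman randomised to Dilapan-S in whom no rod can be placed.
- No misoprostol afterwards: she meets neither entry condition in SAP 6.2.1 and is absent from the safety tables.
- Misoprostol afterwards: she enters, but under misoprostol, because grouping follows actual treatment.

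Either way she is missing from the Dilapan-S column of the table of insertion complications. A laceration or vasovagal reaction during her attempt is missing from it too. No assumed rate is needed for this conclusion. For scale only: with 322/2 = 161 women per arm, assumed failure rates of 2%, 5% and 10% correspond to about 3, 8 and 16 women.

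**2. The plan's own sample size**

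Inputs from the Protocol, Study Design: "Assuming a rate of vaginal delivery within 36 hours to be 65% for Misoprostol and 71% for mechanical method"; margin 10 points; "The study is powered at 85% for detecting the primary outcome with a type 1 error at 2.5% for one-sided test".

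n per arm = (0.65×0.35 + 0.71×0.29) × (1.960 + 1.036)² / (0.71 − 0.65 + 0.10)² = 0.4334 × 8.978 / 0.0256 = 152.0 (unrounded 152.001), so 153. Power at 153 per arm is 85.2%. For the total, 306 × 1.05 = 321.3, so 322 (306/0.95 = 322.1). The stated figures are reproduced, and the proposed changes do not alter them.

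**3. If women with failed insertion were dropped**

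Assumptions, not in the documents: failure rate f of 2%, 5% or 10%; 36-hour success among failures q = 45%. Type I error is evaluated at the margin, where the true rates are 65% and 55% over all randomised women.
- Rate among successful insertions: s = (0.55 − f×0.45)/(1 − f).
- Shift from dropping failures: s − 0.55.
- SE with 161 per arm: √[(0.65×0.35 + 0.55×0.45)/161] = 0.0543.
- One-sided error: Φ(−1.96 + shift/0.0543).

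| f | s | Shift (points) | One-sided error |
|---|---|---|---|
| 2% | 0.5520 | 0.20 | 2.7% |
| 5% | 0.5553 | 0.53 | 3.1% |
| 10% | 0.5611 | 1.11 | 4.0% |

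With 153 per arm, and the Dilapan-S arm reduced by the dropped women, the last figure is 3.9%; the others are unchanged to this precision.

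**4. If the clock restarted after a failed insertion**

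Further assumption: a restart raises success among failures by 10 points. The shift is f × 0.10 = 0.2, 0.5 and 1.0 points. At 153 per arm the error is 2.7%, 3.1% and 3.8%.

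**5. If all failures were counted as non-events**

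Planning rates, 153 per arm: the Dilapan-S rate becomes (1 − f) × 0.71. Power = Φ[(0.10 + p_D − 0.65)/SE − 1.96], with SE from the two rates. For f = 5%: p_D = 0.6745, SE = 0.0541, 0.1245/0.0541 = 2.30, power 63.4%. For f = 2% and 10%, power is 77.7% and 36.9%.

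For comparison, if failures kept a clock that gave 45% success, the Dilapan-S rate would be 0.7048, 0.6970 and 0.6840, and power 82.7%, 78.4% and 70.1%. So part of the loss comes from the failures themselves and part from the counting rule.

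**The case against.** **On safety.** Failed insertions can be counted among all randomised women under the secondary endpoint, and SAP 7.4 draws on adverse event and device deficiency reports, so cases need not vanish altogether. This is fair as far as it goes. But SAP 6.2.1 still assigns the safety data to a population without these women, and the secondary endpoint does not capture other harm from a failed attempt.

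**On the clock.** A reader might infer that ITT drops Dilapan-S failures or restarts their clock, that only this arm is affected, and that the bias favours the device. The documents do not support that.
- No section prescribes dropping or restarting; SAP 6.2.2 keeps every randomised woman.
- A failed attempt happens at some moment, which can be read as initiation. Only a woman with neither attempt nor dose clearly has no start.
- Under the Protocol's Arm B, misoprostol follows a reassuring 20-minute CTG, so a randomised woman may never be dosed and has the same gap.
- Direction depends on the unstated rule: non-event counting works against Dilapan-S. A caesarean is a non-event under any clock, so timing matters only for women who deliver vaginally.

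A reader might also reach 4.3% error at 5% failures by taking the shift at the planning rates, 0.05 × (0.71 − 0.45) = 1.3 points, and entering it at the margin. That mixes two scenarios: when the overall rate is 55%, the same 45% among failures gives a shift of 0.53 points and 3.1%.

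**Conclusion.** The Safety population is wrong as written. It excludes or reassigns the women whom one of its own endpoints describes, so failed insertion and its harms are under-counted for Dilapan-S. This follows from the text alone.

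The time-zero point is missing detail, not a demonstrated bias. It applies to both arms, probably more often to Dilapan-S because insertion can fail. Its size rests on a failure rate and a success rate that the documents do not give. Over the assumed ranges, dropping failures would take the one-sided error from 2.5% to between about 2.7% and 4.0%, while non-event counting would reduce power. Both parts should be corrected; neither affects the planned sample size.

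**What to change.** 1. **SAP 6.2.1:** define the Safety population as all women with an attempted Dilapan-S insertion or at least one misoprostol dose.
2. **SAP 3.3.2 and 7.4:** report failure to insert and the other insertion complications among all women with an attempted insertion, whatever they received afterwards. State in which column of the general safety tables a woman appears if a failed attempt was followed by misoprostol.
3. **SAP 7.2:** set one time zero for every ITT woman: first insertion attempt or first misoprostol dose, or randomisation if neither occurs. For analysis, it is not reset by re-insertion or change of method. Success is then vaginal delivery within 36 hours of that time for everyone, including women who never start. Use the same wording in SAP 3.1.
4. **Sensitivity analysis:** repeat the primary comparison with all women timed from randomisation.

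The cost is SAP wording plus one data check. The Protocol's Arm A text mentions recording the Bishop score and the number of rods but no attempt time, so its availability in the chart must be confirmed. The Dilapan-S safety and efficacy figures may come out slightly less favourable.
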